16.2 Appendix 2: Specific Renal Alert Criteria and Actions and Event Follow-up

Table 16-4 Specific Renal Alert Criteria and Actions

Serum Event

Serum creatinine increase > 2-fold compared to baseline Consider causes and possible interventions
Follow up within 2-5 days

Urine Event

New onset dipstick proteinuria >=+3 OR Consider causes and possible interventions
Assess serum albumin & serum total protein
Repeat assessment to confirm
Consider drug interruption or discontinuation unless other causes are diagnosed and corrected

New onset dipstick hematuria >=+3 Repeat assessment to confirm
Distinguish hemoglobinuria from hematuria
Urine sediment microscopy
Assess serum Creatinine
Exclude infection, trauma, bleeding from the distal urinary tract/bladder, menstruation
Consider bleeding disorder

For all renal events:

Document contributing factors in the CRF: co-medication, other co-morbid conditions, and additional diagnostic procedures performed

Monitor subject regularly (frequency at investigator's discretion) until either:

Event resolution: sCr within 20% of baseline or

Event stabilization: sCr level with +/-20% variability over last 2 months

17 Cohort Specific Information

This section contains details that pertain to specific cohorts and should be considered as supplementary to information presented in the preceding core protocol sections and respective Investigator Brochures or country-specific product labels for marketed investigational products. If there are no cohort- or treatment-specific details presented for a given topic (e.g. cohort- or treatment-specific eligibility criteria, study restrictions, food effects, etc.), the information in the corresponding section in the core protocol for that topic should be implemented without further adjustment.

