10.2.2 Renal safety monitoring

Once a participant is exposed to study treatment, the following two categories of abnormal renal laboratory alert values should be assessed during the study period:

- Serum creatinine increase > 2 -fold compared to baseline during normal hydration status
- Any one of the following:
 - Urine protein-creatinine ratio (PCR) $\geq 1\text{g/g}$ or $\geq 100\text{ mg/mmol}$, OR
 - New onset dipstick proteinuria $\geq 3+$, OR
 - New onset dipstick hematuria $\geq 3+$ (after excluding menstruation, UTI, extreme exercise, or trauma)

Abnormal renal event findings must be confirmed within 48-72 hours after the first assessment.

Once a participant is exposed to study treatment, renal laboratory alerts or renal safety events should be monitored and followed up by the investigator or designated trial staff as summarized in [Table 16-4](#).

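### Table 16-4 ends renal-specific monitoring on serum creatinine alone, so a urine-only alert with creatinine within 20% of baseline already counts as resolved when it is detected

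*Protocol*

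**What the plan says.** Protocol Section 10.2.2 sets two categories of renal alert. The first is a more than two-fold rise in sCr. The second is any one of three urine findings: a urine protein-creatinine ratio (PCR) of at least 1 g/g, new dipstick proteinuria of at least 3+, or new dipstick hematuria of at least 3+. The urine category carries no creatinine condition. The section requires that "Abnormal renal event findings must be confirmed within 48-72 hours after the first assessment", and says that "renal laboratory alerts or renal safety events should be monitored and followed up by the investigator or designated trial staff as summarized in" Table 16-4.

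Table 16-4 (Section 16.2) lists actions for each event. The proteinuria entry includes "Consider drug interruption or discontinuation unless other causes are diagnosed and corrected". The hematuria entry includes "Assess serum Creatinine" along with sediment microscopy and exclusion of other causes. Then, under "For all renal events", the table says to monitor the participant until one of two conditions holds:

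- "Event resolution: sCr within 20% of baseline or"
- "Event stabilization: sCr level with +/-20% variability over last 2 months"

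Section 4.5 counts the pre-specified renal events among the study's safety measures.

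**The concern.** Both conditions that end monitoring are creatinine conditions, yet three of the four alerts open on urine. For a creatinine alert the rule works: it opens on a large rise in sCr and closes when sCr has come back. For a urine-only alert, the rule ends monitoring on a measure that did not open the event and may never have moved. In the hematuria entry, the creatinine test that is part of the work-up can itself satisfy the end point while the dipstick is still 3+.

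At stake is how long a participant with new heavy proteinuria or hematuria is followed for that finding. A pre-specified alert exists so that follow-up does not depend on case-by-case judgement. Here it falls back on that judgement.

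**Working it through.** The plan gives no figure to reproduce. The check applies the Table 16-4 end points to each alert.

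**Inputs**

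- Alerts (Section 10.2.2): 1 serum + 3 urine = 4. Visible in Table 16-4: 1 serum + 2 urine = 3. The PCR alert has no visible entry there, but it is covered by the clause for all renal events.
- End points (Table 16-4): 2, both on sCr. Number using a urine measure: 0 of 2.
- Let r = sCr at detection / baseline sCr. The creatinine alert is read as r > 2.00. Resolution is read as |r - 1| <= 0.20, that is, 0.80 <= r <= 1.20.

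**Is resolution met when the alert opens?**

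| r at detection | Creatinine alert? | Resolution met? | Consequence for a urine alert at this r |
|---|---|---|---|
| 0.80 | no | yes, deviation 20% | end point met at detection |
| 1.00 | no | yes, deviation 0% | end point met at detection |
| 1.20 | no | yes, deviation 20% | end point met at detection |
| 1.21 | no | no, deviation 21% | monitoring continues, on sCr |
| 1.50 | no | no, deviation 50% | monitoring continues, on sCr |
| 2.00 | no | no, deviation 100% | monitoring continues, on sCr |
| 2.01 | yes | no, deviation 101% | monitoring continues, on sCr |

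A creatinine alert needs a deviation above 100% and so can never meet a 20% limit at opening. A urine-only alert meets it at opening whenever r lies from 0.80 to 1.20, whatever the dipstick or PCR shows. The stabilization condition is an alternative, also on sCr, so it adds no urine requirement.

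**Which repair works?** Compare three end rules in two situations.

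| Situation after a urine-only alert | Present rule (sCr) | Urine measure only | sCr and urine measure |
|---|---|---|---|
| r = 1.00, dipstick still 3+ and not stable | may stop | continue | continue |
| r = 1.50, not yet stable for two months, dipstick has cleared | continue | may stop | continue |

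Substituting a urine criterion for the creatinine one would fix the first case and break the second. At r = 1.50 the participant is below the two-fold alert, so the event is urine-only, and monitoring would end with sCr still 50% up. Only requiring both handles the two cases.

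**What else in the protocol applies to a urine-only alert?**

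- Confirmation at 48-72 hours (Section 10.2.2) and a confirmatory repeat in both urine entries of Table 16-4. These establish that the finding is real; they do not say when it is over.
- Section 8.4.1 requires every abnormal laboratory result to be assessed against the adverse event criteria. Those that qualify must be repeated until normal or no longer clinically significant.
- Section 10.1.1 counts a laboratory result as an adverse event only if it produces signs or symptoms, is judged clinically significant, or needs treatment. It then requires follow-up until the event resolves or is judged permanent.

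The last two give a urine-based end point, but only after the investigator has classed the result as an adverse event.

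**The case against.** The strongest reply is that the adverse event rules already cover this, in mandatory wording. To fall through, an alert must be a new 3+ dipstick result or a PCR of at least 1 g/g. It must be confirmed, with benign causes excluded if it is hematuria. It must come with sCr within 20% of baseline, and still be judged not clinically significant. Many confirmed 3+ results will be classed as adverse events. This stands, and it makes the gap narrow. It does not close it, because the safeguard depends on the judgement that a pre-specified alert is meant to spare.

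It can also be said that Table 16-4 governs only how long to monitor and cancels none of the listed actions. That is right. A reader might infer that persisting proteinuria or hematuria is simply abandoned once creatinine is seen to be normal. The documents do not support that: the confirmation, the work-up and, for proteinuria, the consideration of stopping drug remain due whatever sCr shows, and nothing in the table overrides Sections 8.4.1 or 10.1.1.

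The table was read from PDF and is flattened. The proteinuria entry ends in a loose OR, so a PCR entry may have been lost, and its absence is not held against the plan. The closing rule reads as complete: a choice of two conditions, both present, with no urine criterion visibly cut off. The timing of scheduled urinalysis cannot be seen in the available Table 8-1, so how much routine urine testing would continue is unknown.

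Finally, the SAP (document history, Sections 2.5.4 and 4) records early termination with a single cohort. This limits the practical benefit now; it does not make the rule right.

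**Conclusion.** Wrong as written, and minor. Table 16-4 applies creatinine-only end points to events that Section 10.2.2 defines without reference to creatinine. Any urine-only alert with sCr from 0.80 to 1.20 times baseline meets the resolution criterion at detection; a creatinine alert never does. Three of the four alerts open on urine, and neither end point uses urine.

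This rests on reading the 20% limit as two-sided and inclusive, and on the closing rule being complete as extracted. The documents give no rate of urine alerts, so the number of participants affected cannot be derived.

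The consequence is confined to individual safety follow-up. A reader might infer some effect on the efficacy conclusion; there is none, since the primary analysis of percent-predicted FVC does not use these end points. The remaining benefit of a change is limited to any follow-up still under way and to any reuse of this core protocol text.

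**What to change.** In Table 16-4, keep the two creatinine criteria for all renal events. For urine events (dipstick proteinuria, dipstick hematuria, and the PCR alert of Section 10.2.2), add that monitoring ends only when the urine measure that opened the event has also fallen below its alert threshold, returned to baseline, or stabilized. The documents give no interval for urine stabilization; the sponsor's renal safety experts should set it.

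Table 16-3 already follows this principle: Grade 2 and 3 isolated bilirubin elevations are followed on the liver tests themselves until they return to Grade 1 or below, or to baseline.

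The cost is a few words in one table and a few more repeat dipstick or urine PCR tests in participants who have a urine alert. Both tests are already listed in Table 8-3.

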17.1 Cohort 1 LTP001

Cohort 1 will assess the safety and efficacy of LTP001 in participants with mild to moderate JPE.

Approximately 94 patients will be randomized in a 1:1 ratio to one of the following treatment arms:

- Arm 1: LTP001 mg CCI
- Arm 2: Matching placebo

Figure 17-1 Cohort 1 Study Design

[figure not shown]

R = Randomization

17.1.1 Introduction

This cohort will evaluate LTP001. [\[cc\]](#)

CCI

17.1.2 Background

CCI

Preclinical Data

CCI

Clinical Data

CCI

CCI

Dosing Rationale

CCI

Additional details about dosing and potential risks of LTP001 can be found in the Investigator's Brochure.

Procedural risks

CCI

Potential Benefits

CCI

[figure not shown]
17.1.3 Study Treatment

CCI

Table 17-1

CCI

CCI

17.1.4 Specific Exclusion Criteria

101. Women of child-bearing potential (WOCBP), defined as all women physiologically capable of becoming pregnant, unless they are using highly effective methods of contraception for 3 months prior to screening, during dosing, and until End of Study visit (30 days post last treatment). Highly effective contraception methods include:

- Total abstinence (when this is in line with the preferred and usual lifestyle of the participant. Periodic abstinence (e.g. calendar, ovulation, symptothermal, post-ovulation methods) and withdrawal are not acceptable methods of contraception.
- Bilateral tubal ligation, surgical bilateral oophorectomy with or without hysterectomy, total hysterectomy, or bilateral salpingectomy at least six weeks before taking study treatment. In case of oophorectomy alone, only when the reproductive status of the woman has been confirmed by follow up hormone level assessment is not considered to be of child-bearing potential.
- Male sterilization (at least 6 months prior to screening). For female participants on the study, the vasectomized male partner should be the sole partner for that participant.
- Use of oral, (estrogen and progesterone), injected, or implanted hormonal methods of contraception or placement of an intrauterine device (IUD) or intrauterine system (IUS), or other forms of hormonal contraception that have comparable efficacy (failure rate < 1%), for example hormone vaginal ring or transdermal hormone contraception.

In case of use of oral contraception women should have been stable on the same pill for a minimum of 3 months before taking study treatment.

102. Sexually active males must use a condom during intercourse while taking drug and for 24 hours after stopping study medication and should not father a child in this period. A condom is required to be used also by vasectomized men in order to prevent delivery of

the drug via seminal fluid. In addition, male participants should not donate sperm while taking drug and for 24 hours after stopping study medication.

CCI

17.1.5 Specific Restrictions for Study Participants

No specific restrictions for the LTP001 cohort.

[figure not shown]
17.1.5.1 Prohibited Medications

Use of the treatments displayed in the below table are not allowed.

Table 17-2

CCI

CCI

17.1.6 Permitted concomitant therapy requiring caution and/or action

[figure not shown]
Not applicable for LTP001.

17.1.7 **CCI** [REDACTED]

CCI [REDACTED]

[REDACTED]

Table 17-3 CCI
CCI

17.1.8 Pharmacokinetics

PK samples will be collected at the visits defined in [Table 17-3](#). Follow instructions outlined in the laboratory manual regarding sample collection, numbering, processing and shipment. See the potential use of residual samples for more information.

In order to better define the PK profile, the timing of the PK sample collection may be altered based on emergent data.

PK samples will only be evaluated in participants on active treatment.

LTP001 will be determined by a validated LC-MS/MS method; the anticipated Lower Limit of Quantification (LLOQ) is 0.05 ng/mL.

Concentrations will be expressed in mass per volume units and will refer to the free base.

Concentrations below the LLOQ will be reported as “zero” and missing data will be labeled as such in the Bioanalytical Data Report.

17.1.8.1 Pharmacokinetic analytical method(s)

Descriptive summary of LTP001 plasma concentration data will be provided by treatment, and visit/sampling time point, including the frequency (n, %) of concentrations below the LLOQ and reported as zero.

Summary statistics will include mean (arithmetic and geometric), SD, CV (arithmetic and geometric), median, minimum, and maximum.

Descriptive summary statistics will include mean (arithmetic and geometric), SD, and CV (arithmetic and geometric), median, minimum, and maximum.

Appropriate PK parameters e.g. Cmax, Tmax, and partial AUCs may be assessed using non-compartmental analysis (Certara Phoenix). The sparse sampling may limit potential parameter estimation. A population PK model may also be used for PK analysis.

17.1.9 Exploratory Biomarkers

Sample(s) will be collected at the time point(s) defined in the Assessment Schedule ([Table 17-3](#)). The list may be changed or expanded further, as it is recognized that more relevant or novel biomarkers may be discovered during the conduct of the study. Follow instructions for sample collection, numbering, processing, and shipment provided in the laboratory manual.

Target engagement markers of LTP001 may include but are not limited to [CCI](#) [REDACTED]).

RNA sequencing

The expression of targeted genes will be examined using RNA (or other nucleic acid) analytical technologies, such as expression microarrays, polymerase chain reaction, Nanostring, Next Generation Sequencing techniques, or others.

17.1.10 Specific Study Design Considerations

The post-treatment safety follow-up in Cohort 1 will be 30 (+14) days following the last drug administration.

CCI

Table 17-4 LTP001 Specific Safety Assessments

Test Category	Test Name
Thyroid	Triiodothyronine, Free/Total Thyroxine, Thyroid stimulating hormone
Endocrine Function Tests	Aldosterone, Cortisol, Insulin-like growth factor 1, Adrenocorticotropic hormone, Testosterone

17.1.11 Statistical considerations

17.1.11.1 Sample size calculation

As the first cohort in this platform study, the randomization ratio between the treatment group and placebo group is determined as 1:1. Assuming the drop-off rate of 15% [Raghu et al 2018b](#), 47 patients will be randomized into each treatment group with a total of 94 patients for this cohort. The sensitivity of power to changes in assumptions with different drop off rate is listed in [Table 17-5](#).

Table 17-5 Sensitivity of power to changes in assumptions for N=47 per group

True treatment difference for LTP001 vs Placebo (%)	Power for primary endpoint (type I error around 10%)		
	With 10% drop-out rate (38 per group)	With 15% drop-out rate (40 per group)	With 20% drop-out rate (43 per group)
1.6	64%	65%	65%
1.8	72%	72%	73%
2	79%	79%	80%
2.2	84%	85%	85%
2.4	89%	89%	90%

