12.7.2 Within each cohort

Interim analyses are planned when sufficient participants complete their 26-week post-treatment assessments in each cohort (approximately 50%). Data from participants who have completed their 26-week post-treatment assessment and data from participants who have not completed the treatment epoch but have post-treatment assessments at the time of the IA will be included. The purpose of this unblinded IA is to assess early efficacy and to assess futility. The key endpoint to be evaluated at this IA will be the change from baseline in FVC %predicted.

There will be no pause in enrollment at the time of interim analysis, and participants may continue to be enrolled until the interim analysis is complete.

The Bayesian posterior probability of the treatment effect (treatment – placebo) will be calculated for the endpoint. If there is more than 60% probability that the treatment effect at the end of treatment epoch (26 weeks of treatment) is <0 (treatment worse than placebo), then this will act as evidence to suggest that the investigational product has not had a beneficial effect on the endpoint in this population. This data, together with other key endpoints, will be used to assess whether the cohort could be stopped for futility.

Similarly, if there is enough information at this interim analysis to conclude that there is 90% posterior probability that the treatment effect is >0 (treatment better than placebo) in the endpoint, and there is 50% posterior probability of the treatment effect $> 1.3\%$, then this information, together with other key endpoints, will be used to consider early evidence of efficacy and decision of launching later stage of the clinical trials for the respective investigational product.

If the study is not stopped for futility or for early evidence of efficacy at the time of the IA, the cohort will continue until all participants have completed the cohort.

Within cohort IAs, unblinded interim analysis results will be reviewed by the clinical team. The clinical team may communicate interim results (e.g. evaluation of efficacy criteria or information needed for planning/modifying another study) to relevant Novartis teams and members of the DMC.

No further dissemination of interim results should occur, in particular not with individuals involved in treating the study's participants or assessing clinical data (e.g. ECGs, images, symptoms) obtained in the study.

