12.8 Sample size calculation

12.8.1 Primary endpoint(s)

Without considering the drop-off rate, 40 participants per active treatment group and at least 40 participants on placebo of each cohort will give at least 80% power to detect a treatment improvement in change from baseline in FVC%_p (treatment – placebo) for at least 2% in patients with IPF assuming the standard deviation is around 5%.

The sample size calculation is based on the primary efficacy endpoint of change from baseline in FVC%_p at week 26. The criteria for this calculation aimed for a 90% level of proof that difference in change in FVC%_p from baseline to week 26 between treatment and placebo and the mean treatment effect is at least 1.3% better than placebo effect with 50% probability. The former targets proof that the treatment produces a statistically significant improvement in change from baseline in FVC, while the latter targets proof of clinical relevance.

The sample size calculation also takes into account the interim analysis step with futility and early efficacy criteria defined in [Section 12.7](#). The overall type I error at the end of study will be approximately 13%.

Additional participants may be enrolled if more than 15% of the planned randomized participants have not completed the 26 weeks of treatment, as per protocol requirements. Prior to enrolling additional participants, a DMC review of safety data will occur to ensure there are no tolerability/safety issues that would advise against enrolling additional participants.

Refer to [Section 17](#) for cohort specific sample size after considering drop off rate and randomization ratio between the treatment group and placebo group.

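### Protocol Table 17-5 exchanges its 10% and 20% drop-out labels, and prints 79% power where section 12.8.1 states no less than 80%

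*Protocol*

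**What the plan says.** Protocol 17.1.11.1 assumes 15% drop-out and states that "47 patients will be randomized into each treatment group with a total of 94 patients for this cohort". Table 17-5, titled for 47 per group, then gives power at five true differences under three drop-out rates. The outer columns are headed "With 10% drop-out rate (38 per group") and "With 20% drop-out rate (43 per group"). The middle column pairs 15% with 40 per group. The spanning header reads "Power for primary endpoint (type I error around 10" per cent).

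The general calculation is in Protocol 12.8.1. Before any allowance for drop-out, "40 participants per active treatment group and at least 40 participants on placebo of each cohort will give at least 80% power to detect" an improvement of 2 points or more in FVC%p, with a standard deviation of about 5. It adds that "The sample size calculation also takes into account the interim analysis step with futility and early efficacy criteria" of section 12.7, and that "The overall type I error at the end of study will be approximately 13" per cent.

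SAP section 3 contains no calculation and refers to these two protocol sections.

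**The concern.** The table's only purpose is to show what drop-out does to power, and it shows the wrong direction. This bears on a decision in the protocol: section 12.8.1 allows extra enrolment if more than 15% of the planned participants fail to complete 26 weeks. Someone consulting Table 17-5 to judge the cost of passing 15% would read that power goes up.

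The two power statements also disagree for what appears to be the same case: 40 against 40 and a difference of 2. If the discrepancy were large, the justification for the sample size would be in doubt, so its size needs checking.

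**Working it through.** **1. Drop-out labels.** Inputs from Protocol 17.1.11.1: 47 per group; rates 10%, 15% and 20%; printed sizes 38, 40 and 43. Evaluable n = 47 × (1 − d), rounded up.

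| Drop-out | 47 × (1 − d) | Rounded up | Printed |
|---|---|---|---|
| 10% | 42.3 | 43 | 38 |
| 15% | 39.95 | 40 | 40 |
| 20% | 37.6 | 38 | 43 |

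In reverse, the printed sizes imply drop-out of 1 − 38/47 = 19.1%, 1 − 40/47 = 14.9% and 1 − 43/47 = 8.5%.

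**2. Is the label wrong, or the power?** Printed powers for the 38 and 43 columns, by true difference:

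| Difference | 38 per group | 43 per group | Gap (points) |
|---|---|---|---|
| 1.6 | 64% | 65% | 1 |
| 1.8 | 72% | 73% | 1 |
| 2.0 | 79% | 80% | 1 |
| 2.2 | 84% | 85% | 1 |
| 2.4 | 89% | 90% | 1 |

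The larger size has the higher power in all five rows. Each power therefore belongs with its printed size, and only the drop-out rates are misplaced.

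**3. Planned size.** 40/(1 − 0.15) = 47.06. Strict rounding up would give 48, but 47 leaves 39.95 evaluable, which is 40 for practical purposes. The 15% column is labelled correctly.

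**4. The 79%.** A two-sample comparison with 40 per group, SD 5, one-sided 10% level and difference 2 gives only 69.4%, so the printed figure does not come from that simple formula at the documented SD. The documented design was therefore simulated, with 400,000 trials per cell.

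- Data: week-26 mean changes, SD 5, true placebo change −3 (the expected decline in Protocol 12.4.2).
- Placebo prior: the Table 12-1 mixture with weights W, means M and SDs S. Given placebo mean y_P on n participants, component k has posterior variance v_k = 1/(1/S_k² + n/25), posterior mean m_k = v_k(M_k/S_k² + n·y_P/25), and weight w_k proportional to W_k times the normal density of y_P with mean M_k and variance S_k² + 25/n.
- Active arm: flat prior, so the posterior is normal with mean y_T and variance 25/n.
- Then P(effect > c) = Σ w_k Φ[(y_T − m_k − c)/√(v_k + 25/n)].
- Success: P(effect > 0) at least 0.90 and P(effect > 1.3) at least 0.50.
- Interim at half the participants with the section 12.7.2 rules: same efficacy rule; futility if P(effect < 0) exceeds 0.60, treated as binding. An interim efficacy crossing counts as success.

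Results at a difference of 2:

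| n per group | Printed | Simulated power | Simulated type I error |
|---|---|---|---|
| 38 | 79% | 78.0% | 12.1% |
| 40 | 79% | 79.2% | 12.0% |
| 43 | 80% | 80.4% | 11.7% |

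Repeat runs at n = 40 gave 79.2% to 79.4%. Over all 15 cells of the table the largest discrepancy is 2.0 points (difference 1.6, n = 43: 67.0% against 65%). The simulation thus reproduces the printed 79% and falls just short of 80%.

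**5. The two type I error figures.** At n = 40 and SD 5, a flat prior with a single look gives 10.0% error (power 69.5%). The Table 12-1 prior with the interim gives 12.0%. The first equals the nominal level of the 90% criterion; the second is close to the 13% in section 12.8.1.

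**The case against.** Could the exchange come from reading the PDF? No: each rate and its size stand in the same header phrase, so a shifted column cannot produce it.

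On the power statement, the opposing case is stronger. Section 12.8.1 is platform-wide text. It allows more than 40 on placebo and a difference above 2, and gives the SD only approximately, whereas Table 17-5 concerns Cohort 1 at 1:1. The table shows whole percentages, and the gap is 1 point. It stands that this is a matter of wording or rounding. It does not remove the conflict: the section 12.8.1 statement includes 40 against 40 at a difference of exactly 2, and a value printed as 79% is below 80% whether rounded or truncated.

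A reader might go further and infer that the 10% in the table header contradicts the 13% in section 12.8.1. The documents do not support that. The 13% is labelled as overall and follows directly on the sentence about the interim; the header's 10% matches the 90% criterion. Section 12.8.1 also says that the sample size calculation allows for the interim. What is missing is a line connecting the two figures. The documents also do not state whether an interim efficacy crossing counts as success in these calculations: section 12.7.2 says only that such a result "will be used to consider early evidence of efficacy and decision of launching later stage of the clinical trials" for the product.

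Finally, the SAP has dropped the interim analysis and placebo pooling after early termination, so no remaining analysis uses the table. That lowers the stakes to the accuracy of the record, which SAP section 3 still adopts by reference.

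**Conclusion.** The label exchange is certain; it follows from 47 and the printed rates alone. Its effect is 1 point in every row, in the wrong direction. The conflict between 79% and 80% or more is real and also about 1 point. It should not be read as showing that the cohort is too small: 47 per group rests on the correctly labelled column, and the success rule and analysis are unaffected. The relation between 10% and 13% is a request for clarification only.

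The simulated figures are a check and do not identify the sponsor's own calculation. They reduce the random-slope model to week-26 means, apply the Table 12-1 prior to the 26-week change, place the interim at exactly half, treat futility as binding, and set the true placebo change at −3, on which both power and error depend. They also count an interim efficacy crossing as success. If it is not counted and futility is kept, the same runs at n = 40 give 75.2% power and 7.8% error, so the sponsor should state this convention. The label finding depends on none of these assumptions.

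**What to change.** - In Table 17-5, exchange the two outer drop-out labels so that they read 10% (43 per group), 15% (40 per group) and 20% (38 per group). Keep every printed power with its sample size and reorder the columns if wished.
- In section 12.8.1, replace the statement of 80% power or more with about 80% (79% in Table 17-5).
- Under the table, add one line from the sponsor's own calculation saying how the header's 10% relates to the overall 13%, and whether an interim efficacy crossing counts as success.

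The cost is two labels, one phrase and one line. Sample size, success rule and analysis stay as they are.
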